5. STUDY PHASES FROM SCREENING TO END OF STUDY

5.1. Screening

As part of the Screening Visit, study center personnel will explain to the potential patient all aspects of the study, obtain signed informed consent, and document the informed consent process in the patient's source documents before any study-specific procedures are conducted. The signed ICF initiates screening that must occur within 28 days before Day 1.

Required screening assessments, some with shorter screening windows, are listed in [Appendix 1](#). Assessments obtained within 7 days of Day 1 do not have to be repeated on Day 1. Patient treatment authorization may occur as late as Day 1 before the first dose of pamiparib. Results of standard of-care tests or examinations performed before obtaining informed consent and within the screening windows may be used and do not have to be repeated as long as they meet protocol specifications.

The investigator and study center radiologist will assess the potential patient for eligibility. Repeating screening assessments within the original screening window is allowed if the patient did not previously meet certain eligibility criteria. Tumor assessments should not be repeated. Screen failures and consent withdrawals will be documented in the patients' source documents.

5.2. Enrollment

After consent has been obtained, each patient will be assigned a unique patient number that cannot be reassigned to any other patient. Patient numbers will be assigned in chronological order starting with the lowest number. After determination of eligibility, the investigator will complete the supporting documentation and provide them to the sponsor and/or designee for review and subsequent approval. No eligibility waivers will be granted.

5.3. Treatment Phase

The treatment phase is defined as the time elapsed between the first dose of pamiparib and the last dose of pamiparib administered.

Day 1 of Cycle 1 is the first day of pamiparib administration (there is no Day 0 in this protocol). Patients must initiate study treatment within 4 days after authorization for treatment.

Study procedures of each clinic visit are outlined in [Appendix 1](#).

Assessments should be obtained before pamiparib administration unless stated otherwise in [Appendix 1](#) and should be performed in order of least invasive to most invasive assessment. All safety-related assessments must be reviewed and dose modifications, if necessary, be made by the investigator or subinvestigator before pamiparib administration.

Patient-reported outcome questionnaires should be completed before any other study activities occur.

Pamiparib dosing should be interrupted if at least 1 of the reasons listed in [Section 5.5.1](#) is present, and the reason(s) for interruption should be recorded in the source document and in the corresponding electronic case report form (eCRF).

5.4. Unscheduled Visit

Unscheduled visits may occur at any time as necessary as per investigator decision or patient's request for reasons such as assessment or follow up of AEs. Study assessments of an unscheduled visit should be performed based on the reason for the unscheduled visit and are outlined in [Appendix 1](#). If PD is suspected, imaging studies should be performed and blood for biomarkers should be obtained as appropriate.

5.5. Permanent Discontinuation of Pamiparib

5.5.1. Reasons for Permanent Discontinuation of Pamiparib

Patients may permanently discontinue pamiparib for any of the following reasons:

- PD
- AEs
 - AEs that could lead to discontinuation of study drug are described in [Table 4](#) within [Section 6.1.4](#)
- Major protocol deviation
- Patient withdrew consent for study treatment
 - Patients may voluntarily withdraw consent from study treatment at any time
 - Patients should be requested to participate in the follow-up phase, if patient withdraws consent from the treatment phase only
- Investigator's discretion
- Initiation of new anticancer therapy

The reason for permanent discontinuation of pamiparib will be recorded on the eCRF. Patients may discontinue pamiparib for other reasons but these will result in premature discontinuation from study ([Section 5.6.4](#)).

5.5.2. End-of-Treatment Visit

The EOT Visit should occur within 7 days after pamiparib has been permanently discontinued. Required assessments are listed in [Appendix 1](#). A visit should be scheduled as soon as possible, but the EOT Visit may occur later after discussion with the medical monitor for specific circumstances, such as prolonged hospitalization. The visit at which tumor assessments showed PD may be used as the EOT Visit if all required assessments were performed. Tumor assessments do not have to be repeated if they were performed within 14 days of the EOT Visit or at a prior response evaluation that documented PD. An ECG does not have to be repeated if it was performed within 14 days of the EOT Visit.

5.6. Follow-Up Phase

5.6.1. Safety Follow-up

All patients who permanently discontinue pamiparib and have not initiated new anticancer therapy will be followed for AEs and SAEs as outlined in [Section 9.3.1](#). Approximately 30 days after the last dose of pamiparib or before initiation of new anticancer therapy, whichever occurs first, the Safety Follow-up Visit will occur with the safety assessments outlined in [Appendix 1](#). If new anticancer therapy is inadvertently initiated before the Safety Follow-up Visit (eg, without the knowledge of the study center team), a Safety Follow-up Visit should be scheduled as soon as possible.

For patients who do not want to or cannot return to the clinic for the Safety Follow-up Visit, the patient should be contacted by telephone for a review of AEs. If these attempts of contact are unsuccessful, the additional attempts detailed in [Section 5.6.3](#) should be made.

5.6.2. Long-term Follow-up

Patients will be followed for survival and initiation of new anticancer therapy via telephone contact or other means (eg, clinic visit) approximately every 12 weeks ([Appendix 1](#)).

Patients who do not have objective disease progression at the time of pamiparib permanent discontinuation but meet other discontinuation criteria (eg, discontinued for AE and no new anticancer therapy) will continue to have tumor and PSA assessments every 12 weeks and 4 weeks (± 7 days), respectively, until PD or any other reason listed in [Section 5.6.4](#), whichever occurs first. For efficacy assessments as per protocol, refer to [Section 7.3](#) and [Appendix 1](#). If the patient refuses to return for these PSA and tumor assessments or is unable to do so, every effort should be made to contact the patient by telephone to determine the patient's disease status and survival.

5.6.3. Lost to Follow-up

If a patient is lost to follow-up, study center personnel must do their utmost to re-establish contact with the patient and determine the reason for withdrawal. All measures taken to follow up with the patient should be recorded.

Should attempts to contact the patient by telephone be unsuccessful, the following additional attempts should be made to obtain protocol-required follow-up information. The patient should be contacted by mail in a manner that provides proof of receipt by the patient. If unsuccessful, other contacts should be explored, such as referring physicians or relatives. Attempts of contact should be documented in the patient's source documents. If a patient cannot be contacted despite all attempts, the patient will be considered lost to follow-up, and death information should be obtained through a public record search if local agencies permit.

5.6.4. Patient Discontinuation From Study (End of Study for an Individual Patient)

Premature discontinuation from the study (without EOT and any follow-up visits) will occur under the following circumstances:

- Patient withdrew consent for study participation

- Patients may voluntarily withdraw consent from the study at any time
- Investigator's discretion
- Lost to follow-up
 - Lost to follow-up should be recorded as such in the eCRF
 - The investigator should show due diligence by documenting in the source documents steps taken to contact the patient ([Section 5.6.3](#))
- Death
- Study termination by sponsor
- Other, as per the discretion of the sponsor or health authority

When a patient withdraws before the end of the study, the reason for withdrawal should be recorded in the source document and eCRF. Patients who withdraw from the study will not be replaced.

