CLINICAL STUDY PROTOCOL

Protocol Title: A Phase 2, Open-Label, Single-Arm Study of Pamiparib (BGB-290) for the Treatment of Patients with Metastatic Castration-Resistant Prostate Cancer (mCRPC) with Homologous Recombination Deficiency (HRD)

Protocol Identifier: Pamiparib (BGB-290-202)

EudraCT Number: 2018-002587-28

Phase: 2

Protocol Version 0.0: 27 July 2018

Protocol Version 1.0: 16 October 2018

Sponsor: BeiGene, Ltd.
c/o BeiGene USA, Inc.
[name]
[name]
USA

**Sponsor Medical
Monitor:**

████████████████████
████████████████████
████████████████████

Confidentiality Statement

This document contains confidential information and is the proprietary property of BeiGene Ltd. This document is for use by individuals and their designated representatives for their confidential review, consideration, and/or participation in investigational trial(s). This document may not be copied or distributed for review by any unauthorized individuals without the prior written authorization of BeiGene Ltd. Your acceptance of this document constitutes agreement that you will not disclose the information contained herein to others without the prior written authorization from BeiGene Ltd.

FINAL PROTOCOL APPROVAL SHEET

A Phase 2, Open-Label, Single-Arm Study of Pamiparib (BGB-290) for the Treatment of Patients with Metastatic Castration-Resistant Prostate Cancer (mCRPC) with Homologous Recombination Deficiency (HRD)

BeiGene Approval:

Sponsor Medical Monitor

Date

SYNOPSIS

Name of Sponsor/Company:	BeiGene, Ltd.
Investigational Product:	Pamiparib (BGB-290) capsule
Title of Study:	A Phase 2, Open-Label, Single-Arm Study of Pamiparib (BGB-290) for the Treatment of Patients with Metastatic Castration-Resistant Prostate Cancer (mCRPC) with Homologous Recombination Deficiency (HRD)
Protocol No:	BGB-290-202
Number of Patients:	Approximately 100 patients
Study Centers:	Approximately 45 centers in Asia, Australia, Europe, and the United States
Study Phase:	2
Treatment Duration:	Patients will receive daily treatment during the study until occurrence of progressive disease (PD), unacceptable toxicity, death, withdrawal of consent, lost to follow-up, or study termination by sponsor.

Study Objectives:

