5.7. End of Study

The end of study is defined as the last patient last visit at the end of the long-term follow-up phase. This is the last timepoint for data collection. A patient is considered on study as long as the patient is still in long-term follow-up.

The sponsor has the right to terminate this study at any time. Reasons for terminating the study early may include, but are not limited to, the following:

- The incidence or severity of AEs in this or other studies indicates a potential health hazard to patients
- Overall patient enrollment is unsatisfactory
- Data recording is inaccurate or incomplete
- Evidence of no clinical benefit

The sponsor will notify each investigator if a decision is made to terminate the study. Should this be necessary, prematurely discontinued patients should be seen as soon as possible for an EOT Visit and Safety Follow-up Visit.

The investigators may be informed of additional procedures to be followed to ensure that adequate consideration is given to the protection of the patient's interests. The investigator will be responsible for informing IRBs/IECs of the early termination of the study.

The sponsor has the right to close a study center at any time. The decision will be notified to the center in advance. Reasons for closing a center may include but are not limited to the following:

- Excessively slow recruitment
- Poor protocol adherence
- Inaccurate or incomplete data recording

- Good Clinical Practice noncompliance
- Study activity is completed (ie, all patients have completed and all obligations have been fulfilled)]

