9.1.4. Follow-Up of Adverse Events

After the initial AE or SAE report, the investigator is required to proactively follow each patient and provide further information to the sponsor on the patient’s condition.

All AEs and SAEs documented at a previous visit/contact and designated as ongoing will be reviewed at subsequent visits/contacts.

All AEs and SAEs will be followed until resolution, the condition stabilizes or is considered chronic, the AE or SAE is otherwise explained, the patient is lost to follow-up, or the patient withdraws consent. Once resolved, the appropriate AE or SAE eCRF page(s) will be updated. The investigator will ensure that follow-up includes any supplemental investigations as may be indicated to elucidate the nature and/or causality of the AE or SAE. This may include additional laboratory tests or investigations, histopathologic examinations, or consultation with other health care professionals.

The sponsor may request that the investigator perform or arrange for the conduct of supplemental measurements and/or evaluations to elucidate as fully as possible the nature and/or causality of the AE or SAE. The investigator is obligated to assist. If a patient dies during participation in the study or during a recognized follow-up period, the sponsor will be provided with a copy of any postmortem findings, including histopathology if conducted.

New or updated information will be recorded on the originally completed SAE report/eCRF, with all changes signed and dated by the investigator. The updated SAE follow-up report/eCRF should be resent to the sponsor within the timeframes outlined in [Section 9.5.1](#).

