9.3. Timing, Frequency, and Method of Capturing Adverse Events and Serious Adverse Events

9.3.1. Adverse Event Reporting Period

After the ICF has been signed, but before initiation of pamiparib, only SAEs should be reported to the sponsor.

After initiation of treatment, all AEs and SAEs, regardless of relationship to treatment, will be reported until 30 days after the last dose of pamiparib or initiation of new anticancer therapy, whichever occurs first. After this period, the investigator should report any SAEs that are believed to be related to prior study drug treatment.

After a patient is discontinued from the study, investigators are not obligated to actively seek AEs or SAEs from the former patients. However, if the investigator learns of any SAE, including a death, at any time, and considers the SAE related to pamiparib, the investigator will notify the sponsor.

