- l. Following the screening tumor assessment, tumor assessments will occur at the schedule of every 8 weeks (± 7 days) after Day 1 for the first 24 weeks, then at the schedule of every 12 weeks (± 7 days). Any measurable disease must be documented at screening and reassessed at each subsequent tumor evaluation. The same imaging method(s) used at screening must be used throughout the study. A documented standard-of-care tumor assessment may be used as the screening assessment provided it meets protocol requirements ([Section 7.3.1.2](#)). CT scan with intravenous contrast is the preferred imaging method for assessment of chest, abdomen, and pelvis. Other imaging methods are allowed as outlined in [Section 7.3.1.2](#). Imaging of other areas of disease should be performed every 8 weeks ± 7 days for 24 weeks, then every 12 weeks ± 7 days. Patients without PD at the EOT Visit should be followed with tumor

assessments every 12 weeks (± 7 days) during the long-term follow-up phase.

- m. Whole-body radionuclide bone scan must be performed at screening and will then occur at the schedule of every 8 weeks (± 7 days) after Day 1 for the first 24 weeks, then at the schedule of every 12 weeks (± 7 days). Patients without PD at the EOT Visit should be followed with bone scans every 12 weeks (± 7 days) during the long-term follow-up phase.
- n. MRI scan of the brain to assess for brain metastases must be performed at screening if the patient has symptoms that could be due to brain metastases. CT scan with intravenous contrast is acceptable if MRI is not available or the patient is claustrophobic. If brain metastases are present at baseline, the patient is eligible for this study if criteria listed under Exclusion Criterion 8 are met.
- o. AEs and laboratory safety measurements will be recorded at each study visit, graded per National Cancer Institute-Common Terminology Criteria for Adverse Events Version 4.03 or higher, and assessed as outlined in [Section 9](#). After the informed consent form has been signed, but before initiation of pamiparib, only SAEs should be reported. After initiation of pamiparib, all AEs and SAEs, regardless of relationship to pamiparib, will be reported until 30 days after last dose of pamiparib or initiation of new anticancer therapy, whichever occurs first. After this period, the investigator should report any SAEs that are believed to be related to pamiparib.

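### Protocol Sections 5.6.4 and 5.7 give opposite visit instructions when the sponsor terminates the study, and no text says which prevails

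*Protocol*

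**What the plan says.** Protocol Section 5.6.4 defines the end of study for an individual patient. It states: "Premature discontinuation from the study (without EOT and any follow-up visits) will occur under the following circumstances". Termination by the sponsor is one of the listed items, beside withdrawal of consent, investigator's discretion, loss to follow-up, death and a residual category. That bullet carries no exception and no reference to Section 5.7.

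Section 5.7 covers the sponsor's decision to terminate and the notice to investigators. It then says that "prematurely discontinued patients should be seen as soon as possible for an EOT Visit and Safety Follow-up Visit".

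Other protocol text bears on the same patients:

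- The Synopsis row on treatment duration ends with "withdrawal of consent, lost to follow-up, or study termination by sponsor", so sponsor termination also ends dosing.
- Section 5.5.1 lists reasons for stopping pamiparib. Sponsor termination is not among them. Stopping for a reason outside the list is said to lead to premature discontinuation from the study, with a reference to 5.6.4.
- Section 3.1 cites both 5.5.1 and 5.6.4 for the end of treatment, and then expects an EOT Visit within 7 days, followed by safety and long-term follow-up.
- Section 5.5.2: "The EOT Visit should occur within 7 days after pamiparib has been permanently discontinued".
- Section 5.6.1: "All patients who permanently discontinue pamiparib and have not initiated new anticancer therapy will be followed for AEs and SAEs".

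**The concern.** One event carries two opposite instructions, and both sections describe the patients in the same terms, as prematurely discontinued. A site that looks up sponsor termination in 5.6.4 finds no visits. A site that looks it up in 5.7 finds two.

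What is at stake is safety ascertainment after the last dose. Protocol Section 10.5.2 and SAP Section 6.5.2 count treatment-emergent adverse events to 30 days after pamiparib stops, or to new anticancer therapy if that comes first. In Appendix 1 the EOT and Safety Follow-up columns are the two scheduled post-treatment visits with hematology and chemistry. SAP Section 8 records that the trial was terminated after 13 patients, drops the efficacy analyses and keeps the safety analyses as planned. Safety is therefore the output that the conflict could touch.

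**Working it through.** No formula applies, and the plan gives no figure to reproduce. The check sets the texts side by side and then counts visits.

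**Step 1. What each text requires when the sponsor terminates.**

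| Protocol text | EOT Visit | Safety Follow-up Visit |
|---|---|---|
| 5.6.4, sponsor-termination bullet | No | No |
| 5.7, sponsor termination | Yes | Yes |
| 3.1, end of treatment (cites 5.5.1 and 5.6.4) | Yes, within 7 days | Yes, as a later phase |
| 11.4, early closure of the study | Silent (data and drug supplies only) | Silent |

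The first two rows conflict directly. The third row agrees with 5.7.

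**Step 2. Where the cross-references lead.** Section 5.5.1 points to 5.6.4 for any reason not on its list, and sponsor termination is such a reason. Section 5.5.1 does not point to 5.7. A site that follows the references arrives at the no-visit rule.

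**Step 3. Whether a precedence rule exists.** None appears in 5.5, 5.6, 5.7, 9.3.1, 11.4 or the notes to Appendix 1.

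**Step 4. Visits lost per patient if 5.6.4 is applied literally.** Total = EOT Visit omitted + Safety Follow-up Visit omitted.

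| Patient's position at termination | EOT | Safety Follow-up | Total |
|---|---|---|---|
| On pamiparib or just stopped, neither visit done | 1 | 1 | 1 + 1 = 2 |
| EOT Visit done, or a progression visit has served as it (allowed by 5.5.2); Safety Follow-up still due | 0 | 1 | 0 + 1 = 1 |
| Safety Follow-up already completed | 0 | 0 | 0 + 0 = 0 |

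The range is 0 to 2 visits per patient. The number of laboratory sets lost can be smaller than the number of visits. Section 5.6.1 allows adverse events to be reviewed by telephone when a patient does not want to return or cannot, and such a contact yields no hematology or chemistry.

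**Step 5. Number of patients.** The documents do not say how many of the 13 patients were on pamiparib, or within 30 days of the last dose, at termination. A total over patients cannot be calculated.

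**The case against.** The strongest reply is that the documents lean clearly one way. Section 5.7 deals with sponsor termination specifically and is tied to the sponsor's notice to investigators. Section 5.6.4 is a generic list that also covers death and loss to follow-up, where visits are impossible, so its parenthesis may be no more than a description. Section 3.1 expects an EOT Visit even when treatment ends for a 5.6.4 reason. This stands as far as likelihood goes: a careful site would probably hold the visits. It does not remove the conflict. The bullet in 5.6.4 names sponsor termination as explicitly as 5.7 does, 5.7 is worded as a recommendation, and the reader has to infer the order of precedence.

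A second reply is that adverse event duties continue without the visits. Under note o of Appendix 1, adverse events "will be reported until 30 days after last dose of pamiparib or initiation of new anticancer therapy". Section 9.3.1 sets the same period. Section 9.1.4 adds: "After the initial AE or SAE report, the investigator is required to proactively follow each patient". This also stands, and it limits the consequence. It does not replace a blood draw. Anemia and neutropenia were among the hematologic events in the earlier pamiparib study (Section 1.5.2.3), and a low count without symptoms is found only if blood is taken.

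A reader might go further and infer that 9.3.1 releases sites inside the 30 days, because it says: "After a patient is discontinued from the study, investigators are not obligated to actively seek AEs or SAEs from the former patients". The order of that section does not support this. It first sets the 30-day duty, then addresses related serious events after that period, and only then speaks of former patients. Note o repeats the 30-day duty without the release.

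**Conclusion.** The conflict between 5.6.4 and 5.7 is real, and the protocol is wrong as written on this point. It is minor. Its size is 0 to 2 scheduled post-treatment safety visits per patient, on the assumption that a site applies 5.6.4 literally. The number of patients is unknown. No primary endpoint, hypothesis, analysis set or error rate is affected.

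Three stronger readings are tempting and are not supported:

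- **That safety data in this trial are incomplete.** SAP Section 8 shows that the trial ended early. It does not show that anyone was on drug at that time, that any site acted under 5.6.4, or that any visit was missed.
- **That every affected patient loses two visits and two laboratory sets.** Two is the upper limit. The count depends on the patient's position at termination and on the allowances in 5.5.2 and 5.6.1.
- **That 5.5.2 and 5.6.1 are further independent contradictions.** Neither makes an exception for sponsor termination, but 5.5.1 arguably takes these patients out of both sections by sending them to 5.6.4. Notes d and e of Appendix 1 largely repeat those two sections. The secure conflict is 5.6.4 against 5.7.

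**What to change.** In Section 5.6.4, remove sponsor termination from the rule that omits visits. Alternatively, keep the bullet and add: *except that the EOT Visit and Safety Follow-up Visit apply per Section 5.7*.

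Leave Section 9.3.1 unchanged. The 30-day reporting duty is already there. Tying the release from active inquiry to the end of that period would place a new duty on patients who leave at the investigator's discretion or for other reasons, which this conflict does not involve.

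The cost is one clause. It adds no visit that 5.7 does not already request, and 5.6.1 already provides for a telephone review when a patient cannot attend. Because the trial has been terminated, the new wording cannot change what was done. It corrects the text for reuse, and the sponsor can separately confirm that patients on pamiparib at termination had both visits.
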